6.1 Clinical Evaluations	17
6.2 Laboratory Evaluations.....	17
6.3 HCV and HIV Virologic Studies	18
7 Potential Risks and Benefits	19
7.1 Potential Risks.....	19
7.2 Potential Benefits.....	20

TABLE OF CONTENTS

8	Stored Samples and Future Research.....	20
9	Assessment of Safety & Monitoring	21
9.1	Recording/Documentation	22
9.2	Definitions.....	22
9.2.1	Reporting Protocol Deviations, AEs and Deaths	22
9.2.2	Annual Reporting to the IRB.....	22
9.3	Type and Duration of the Follow-up of Subjects after Adverse Events.....	23
9.4	Withdrawal of a Subject.....	23
9.5	Return of Withdrawn/Removed Subjects	23
10	Remuneration Plan for Subjects.....	24
11	Statistical Considerations	24
11.1	Sample size	24
11.2	Description of the Analyses	24
12	Ethics/Protection of Human Subjects	24
12.1	Informed Consent Process	24
12.1.1	Illiteracy and Consenting.....	25
12.2	Subject Confidentiality	25
	Appendix A: Scientific References	25
	Appendix B: Schedule of Procedures/Evaluations	28

List of Abbreviations

AE	Adverse Event/Adverse Experience
Coinfection	Identifier for those with both HIV and hepatitis B or C
DAA	Directly Acting Antiviral
ART	Highly Active Anti-retroviral Therapy
HBV	Hepatitis B Infection
HCV	Hepatitis C Infection
HIPAA	Health Insurance Portability and Accountability Act
MAVERIC	Study short name
IHV	Institute of Human Virology
IRB	Institutional Review Board
N	Number (typically refers to number of subjects/sample size)
PI	Principal Investigator
RT-PCR	Reverse Transcriptase Polymerase Chain Reaction
SAE	Serious Adverse Event/Serious Adverse Experience
SVR	Sustained Virologic Response 12 weeks following therapy
VL	Viral Load
WHO	World Health Organization

Protocol Summary

- Full Title:** **A Pilot Study to Evaluate Anti-HCV Effect of Maraviroc in HIV/HCV Co-infected Patients**
- Short Title:** MAVERIC
- Conducted by:** Institute of Human Virology, University of Maryland
- Principal Investigator:** [name]
- Sample Size:** N= 10
- Accrual Ceiling:** 15
- Study Population:** Adults infected with viral hepatitis C and being treated for HIV infection
- Study Design:** Single-site, longitudinal, open-label, interventional pilot study for evaluation of the effectiveness of Maraviroc on HCV viral levels in patients with HCV and HIV undergoing antiretroviral therapy. Participants will be seen at a IHV Clinic, Baltimore MD 21201.
- Study Duration:** *Start Date:* August 1, 2016
End Date: August 1, 2017.

Recently, in-vitro studies have demonstrated that maraviroc, and HIV ART that exerts anti-HIV effects through CCR5 antagonism, appears to have significant anti-viral effect on HCV replication comparable to sofosbuvir—a potent HCV NS5B inhibitor and the backbone to several combination anti-HCV DAA therapy currently approved. In this study, we propose to characterize the antiviral effect of Maraviroc in HIV/HCV coinfecting patients naïve to anti-HCV DAA therapy. We intend to evaluate HCV viral kinetics after adding maraviroc to existing ART in 10 HIV/HCV coinfecting patients by performing serial HCV RNA measurements. This study will provide the in-vivo evidence that CCR5 antagonists can be used to treat HCV and may offer prolonged effect in the HIV/HCV coinfection by assisting with modulation of hepatic regeneration pathways.

1 Background Information and Scientific Rationale

1.1 Epidemiology

Hepatitis C virus (HCV) is a major cause of chronic liver disease and is the leading indication for liver transplantation in the US. Approximately 4.1 million individuals (1.6%) in the US population have been infected with HCV.⁶ Approximately 50% of HCV infected persons have been tested, with the remainder unaware of their diagnosis. Of those that reach care, 16% have been treated, and 9% have been cured of HCV.^{7 8} Among HIV-positive individuals, coinfection with HCV is relatively high, ranging from 15% to 30%.^{9,10} Liver disease in HIV patients has become a major source of morbidity and mortality in the US and worldwide.¹¹ HIV/HCV coinfection is especially problematic in the US now that HIV patients are living longer on highly active antiretroviral therapy (ART), and are often dying of complications from liver disease primarily related to HCV. In addition, more than 75% of adults in the US infected with HCV were born between 1945 through 1965. As a result, the prevalence of liver disease resulting from HCV is likely to increase over time, adding a significant burden to the medical system. It is expected to continue to rise as more and more people get screened. The impact of chronic HCV on liver failure, HCC and mortality is enormous and continues to increase at an alarming rate. Recent advances in effective pill-only treatment regimens to treat and cure HCV is promising making it feasible to test, link and treat this population effectively.

1.2 Baltimore and Washington DC

Baltimore has been cited as a leading city in terms of injection drug use, ranking second in the nation for intravenous drug use (IVU) per capita in 2004¹². A more recent study looking at patterns of drug use and infectious disease in Baltimore drug users found that 45% of recent users of cocaine or heroin were infected with hepatitis C and with nearly 8% co-infected with HIV¹³.

1.3 Treatment

Until recently, a major limiting factor in expansion of treatment for HCV has been standard of care therapy with pegylated interferon, ribavirin, and more recently for genotype 1 disease, boceprevir and telaprevir. These medications have significant side effect profiles, response-based dosing regimens of over 6 months, and decreased efficacy in key groups including: those with genotype 1 disease, HIV coinfection, and cirrhosis. In particular the response rates observed in HIV/HV coinfecting patients were much lower than those without HIV infection.^{14,15} However, with new therapeutics becoming available, the picture is quite hopeful. There has been dramatic improvement using all oral DAA regimens with sustained virologic response (SVR) rates over 90%, short-duration therapies and well-tolerated, simple regimens including among those with HIV coinfection. Although the rates of SVR has been relatively high in limited studies that have evaluated these novel DAA regimens in HIV/HCV coinfecting patients, it is unclear whether

achieving an SVR will result in regression of liver fibrosis. It is also not understood, at what rate the regression of fibrosis may occur and whether it would occur in all patients regardless of HIV status. In this regard, HIV/HCV coinfecting patients have demonstrated a much more rapid progression of liver fibrosis over time. Hence, management of HIV/HCV coinfecting patients offer several challenges that need to be addressed.

1.4 Rationale

CCR5 is a chemokine co-receptor best known for its central role in HIV binding to T-cells. However, CCR5 is expressed in hepatocytes, stellate cells and Kupffer cells within the liver¹⁶ and may mediate liver fibrosis.¹⁷⁻¹⁹ Interaction between HIV (or gp120) and CCR5 has been shown to upregulate HCV replication as well.²⁰ A recent study hypothesized that CCR5 blockade might modulate HCV replication.²¹ They examined the effect of CCR5 blockade using two potent receptor antagonists, cenicriviroc (dual CCR2/5 antagonist) and maraviroc (CCR5 antagonist), on HCV replication in-vitro. Both agents are known to inhibit HIV replication and cenicriviroc is being evaluated in a Phase 2b trial in adults with NASH and hepatic fibrosis. Briefly, 100,000 Huh7.5_{JFH1} human hepatocyte cells, which constitutively produce a cell-line adapted strain of HCV genotype 2 and express CCR5 were seeded in 24-well format plates. The next day, cells were incubated with 25 ug/ml, 0.25 ug/ml, or 0.0025 ug/ml of the antiviral drugs under investigation. These included maraviroc or cenicriviroc, sofosbuvir (an HCV polymerase inhibitor positive control) or raltegravir (an HIV integrase inhibitor negative control). The culture supernatants were collected after 24 hours of incubation with the drug. Cell number was evaluated to determine if cell viability affected HCV viral load production. HCV replication was monitored using a commercial HCV Core Antigen ELISA assay (Cell BioLabs, San Diego, CA). Negative strand HCV RNA was detected by a qualitative strand-specific RT-PCR assay as a measure of actively replicating virus. Positive strand HCV RNA was measured by qRT-PCR in the cell culture supernatant.

Collectively, CCR5 blockade with cenicriviroc & maraviroc decreased HCV core production, HCV negative strand production and HCV RNA released to supernatant to extents comparable with sofosbuvir, a known HCV NS5B inhibitor with extremely potent anti-HCV activity in-vitro and in-vivo.²² The results were specific to R5 antagonism since Raltegravir (an HIV integrase inhibitor) did not lead to a similar effect on HCV replication. These results led us to believe that CCR5 blockade appears to modulate HCV replication in an *in-vitro* Huh7.5_{JFH1} human hepatocyte cell system. This potent inhibition suggests that CCR5 may represent a new target for multidrug HCV therapy and warrants evaluation in HIV/HCV coinfecting patients. In this regard, we intend to study a small group of HIV/HCV infected patients.

[figure not shown]

Figure 1A – Change in HCV Core Antigen concentrations

A dose-dependent response was observed for maraviroc, cenicriviroc, and sofosbuvir at the 0.25 ug/ml and 25 ug/ml concentrations but not at 0.0025 ug/ml. Raltegravir had no effect on HCV core antigen production, nor did DMSO buffer controls. Cell viability was not affected by any drug or by the DMSO buffer solution.

Figure 1B – Change in HCV Negative Strand RNA quantity

RNA from cell lysates was extracted using the mirVana miRNA Isolation Kit (Ambion) and resuspended in 50 uL of elution buffer. HCV RNA was detected by reverse transcription PCR and primers HCV-II sense (5'-CAC TCC CCT GTG AGG AAC T-3', nucleotides [nt] 38–56 of the 5'UTR) and HCV-I antisense (5'-TGG ATG CAC GGT CTA CGA GAC CTC-3', nt 342–320). Thirty cycles of PCR (94C for 30 sec, 58C for 1 min, and 72C for 2 min) were performed, and PCR products (295 base pairs in length) were visualized by gel electrophoresis. GAPDH (400 bp) was amplified as a control.

Figure 1C – Change in HCV Positive Strand RNA

HCV RNA was measured in the cell culture supernatants after 24 hours of drug incubation. Data shown is the fold change of RNA detected normalized and compared to HCV RNA at baseline.

1.5 Institutional Background

The Institute of Human Virology (IHV) is a world renowned institution dedicated to the study of natural history, pathogenesis, and therapeutics for human viral infection. The IHV has led the field in HIV and HCV pathogenesis and therapeutics for over the past two decades. IHV has spearheaded HIV therapeutics and as a single institution has initiated ART in over 1 million HIV-infected subjects globally. In this study, IHV is partnered with University of Cincinnati with [name] [name], who is a leading hepatologist in the world and a pioneer in studies involving HIV and HCV coinfection. The preliminary data supporting this trial was performed in [name] laboratory.

2 Study Objectives

2.1 Primary Objective

Determine the in-vivo anti-HCV efficacy of Maraviroc in HIV/HCV coinfecting patients.

2.2 Secondary Objectives

1. Determine the viral kinetics of HCV in HIV/HCV infected subjects initiated with maraviroc.
2. Assess the safety and tolerability of adding maraviroc to ART in HIV/HCV coinfecting subject

2.3 Exploratory Objectives

Virologic and Immunologic assays to evaluate changes associated with CCR5 antagonism.

3 Study Design

This is a single-site, open-label, randomized, prospective, cross-over pilot interventional study for evaluating the anti-HCV effect if CCR5 antagonism in HIV/HCV coinfecting patients receiving ART.

3.1 Study Drug

Maraviroc (trade name: **Selzentry**) is an [antiretroviral drug](#) in the [CCR5 receptor antagonist](#) class used in the treatment of [HIV](#) infection. It is also classed as an [entry inhibitor](#). Maraviroc was approved for the treatment of HIV infection by the Food and Drug Administration in 2007. Specifically, maraviroc is a negative [allosteric](#) modulator of the chemokine [CCR5](#) receptor, found on the surface of T lymphocytes. The [chemokine](#) receptor CCR5 is an essential co-receptor for most HIV strains and necessary for HIV to infect lymphocytes. The drug binds to CCR5 at a non-competitive site and alters gp120 binding site of CCR5, thereby blocking the HIV entry into the target cell.²³ Maraviroc is very safe and Phase III clinical trials did not show any difference in the incidence of adverse events in the placebo or maraviroc treated groups.

Dosing

Available as 150 or 300 mg tablets. As per labeling based on concomitant ART (see table 1 below).

Table 1. Maraviroc dosing for participants based on concomitant ART

Background Antiretroviral Therapy Regimen	Maraviroc dose
With NRTI's, tipranavir/ritonavir, nevirapine, raltegravir, and other drugs that are not potent CYP3A inducers nor inhibitors	300mg tablet twice a day
With potent CYP3A inducers including efavirenz (without a potent CYP3A inhibitor)	600mg (two 300mg tablets) twice a day
Boosted protease inhibitor-containing regimen	150mg tablet twice a day

3.2 Research Strategy

Study subjects will be selected and enrolled at a single site at IHV. HIV infected participants (coinfected with HCV and DAA-treatment naïve for HCV) who are well controlled on ART will receive Maraviroc for one month and serial measurements of viral and immune parameters will be performed. Rationale for not recruiting treatment naïve HIV/HCV coinfecting participants is based on previous studies that have demonstrated an increase in HCV VL in HIV/HCV coinfecting patients who initiated ART.²⁴ We believe this will interfere from characterizing the anti-viral effect, if any, of CCR5 antagonism. Hence, we plan to do an interventional study with frequent in-vivo viral kinetic analysis to evaluate anti-HCV effect of CCR5 antagonism.

Patients with HIV/HCV coinfection with HIV viral suppression and active HCV infection will be included. Patients will be randomized to one of 2 cohorts: immediate start of maraviroc (cohort 1), and delayed start (cohort 2). All patients will receive 4 weeks of Maraviroc (dose adjusted according to intake of concurrent CYP 3A inducers, see table 1) in addition to their regular ART. The immediate start group will receive maraviroc in addition to their HIV antiretroviral regimen from week 0 to 4. This will be followed by a wash out period of 4 weeks after cessation of Maraviroc. After the 4-week wash out period, patients will be crossed over the no-maraviroc arm. The delayed start group will receive no maraviroc from weeks 0 to 4, followed by a 4 week wash out period, before crossing over to the on-maraviroc arm. Figure 2 below illustrates the study scheme.

[figure not shown]

Figure 2: Study scheme

3.3 Primary Hypothesis

The primary hypothesis is that CCR5 antagonism will lead to lower HCV viral load. In addition, we hypothesize that CCR5 antagonism using maraviroc will demonstrate significantly lower HCV viral kinetics in the first 7 days of initiation of therapy.

4 Study Population

Patients will have HCV and HIV and receiving HIV therapy using ART as recommended by HIV treatment guidelines. These patients will be selected to receive one month of maraviroc and have serial measurements of viral, safety and immune parameters to evaluate the anti-HCV efficacy of CCR5 antagonism.

4.1 Rationale for Subject Selection

Subjects of both genders will be considered for inclusion in this study. There will be no racial, ethnic, or gender discrimination. Persons in jail or prison are not eligible for this study. Women will not have research procedures while pregnant.

4.2 Subject Inclusion Criteria

To be eligible for participation on this protocol, a participant must satisfy all of the following conditions:

1. Be ≥ 18 years old
2. HCV-infected without plans to undergo HCV treatment for duration of study
3. HIV infected
4. Currently receiving ART with HIV VL < 50 IU/ml for ≥ 12 months
 - a. One virologic blip ≤ 400 copies/ml permissible within the 12 months
5. CD4 T cell counts > 100 cells/mm³
6. Non-cirrhotics and cirrhotics can be included
7. Willing to sign informed consent

An HCV infected individual is defined as any individual with documentation of the following in the past:

- Positive HCV antibody and/or positive HCV RNA test (HCV RNA of 2,000 IU/mL or greater).

Anti-HCV DAA treatment naïve is defined as:

- No previous treatment for HCV with any DAA. Previous exposure to interferon and ribavirin are allowed.

An HIV infected individual is defined as any individual with documentation of the following:

- Positive Enzyme Linked Immunosorbent Assay followed by a positive Western Blot or detectable HIV viral load, or HIV viral < 50 copies/mL with documentation this individual is currently on an active HIV ART.

Cirrhosis is defined as

- FibroTest® score >0.75 OR APRI (AST to Platelet Ratio Index) >2 AND FIB-4 (Fibrosis-4) >3.25 OR FibroScan with a result of >12.5kPa OR liver biopsy showing cirrhosis at any time

Absence of cirrhosis is defined as

- FibroTest® score \leq 0.48 OR APRI \leq 1 AND FIB-4 <1.45 performed within 1 year of screening OR FibroScan with result of \leq 12.5kPa within 1 year of screening OR liver biopsy within 3 years of screening showing absence of cirrhosis.

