5.1 Screening /Enrollment

Screening will occur at the IHV. Subjects who consent to the study will be enrolled. A health history will be reviewed and a physical exam will occur prior to the baseline research lab draw. Outside labs performed within the last six months may be used to determine eligibility.

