5.1.1 Procedures to be performed at Screening/Enrollment

- Complete Medical History
- Complete Physical Examination - including body weight, height, and vital signs (temperature, pulse, respiratory rate, and blood pressure) must be obtained.
- Complete Medication History – A complete review of all medications and supplements the patient is currently taking.
- Urine Pregnancy test for women of child bearing potential
 - Female subjects of childbearing potential will have a urine pregnancy test (HCG) performed prior to the study start date. Women who are found to be pregnant will be excluded from the study.
- Blood for Screening Labs obtained within 6 months of study entry –
 - CBC with differential
 - Serum Chemistry
 - LFT's (including AST, ALT, Total bilirubin)
 - Hepatitis C Quantitative RNA
 - HIV-1 RNA PCR
 - CD4 Cell Count

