5.2 Randomization

Enrolled participants will be randomized to the immediate start or delayed start group in a 1:1 fashion at time of enrollment.

5.3 Day 0 to Day 7

5.3.1 Study visit, all subjects: Baseline Visit – Day 0

Once eligibility is known, *all subjects* will have baseline research sample collection of HCV VL, and PBMC, plasma, serum and Paxgene RNA and DNA for storage. Maraviroc will be initiated for participants randomized to the immediate start group.

5.3.2 Study Visits, immediate start group only: Days 1, 2, 4 and 7

HCV VL will be obtained at days 1, 2, 4 and 7. Day 7 labs can be completed up to 1 day later.

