5.4 Study visit, immediate start group only: Day 14 (Week 2 visit)

HCV VL will be obtained. Safety assessment will be performed (CBC with differential and CD4 and HIV viral loads. Patient reports of adverse effects). Labs can be completed up to 2 days later.

5.5 Study visits, immediate start group only: Day 21/week 3

HCV VL will be obtained. Labs can be completed 2 days later.

5.6 Study visit, both groups: Day 28/week 4

HCV VL and PBMC, plasma, serum and Paxgene RNA for storage will be obtained. Labs can be completed 2 days later.

Immediate start group: Maraviroc will be discontinued at day 28/week 4.

5.7 Washout period, week 4 through to week 8

5.8 Study visit, both groups: Day 56/week 8

HCV VL and PBMC, plasma, serum and Paxgene RNA for storage will be obtained.

Delayed start group: A review of medical history and medication history will be performed to evaluate for any interim changes from screening visit. Physical exam will be performed. HCV VL and PBMC, plasma, serum, and Paxgene RNA for storage will be obtained. Maraviroc will be started.

5.9 Study visits, delayed start group only: Day 57, 58, 60, 63, 70 (week 10), 77 (week 11)

HCV VL will be obtained

Safety assessment at day 70/week 10 (on week 2 after initiating maraviroc).

Weeks 10 and 11 labs can be completed up to 2 days later.

5.10 Study visit, both groups: Day 84/Week 12

HCV VL and PBMC, plasma, serum. and Paxgene RNA for storage will be obtained. Visits can be completed up to 2 days later.

Delayed start group: Maraviroc will be discontinued. Safety assessment.

Immediate start group: **End of study participation.** Safety assessment.

5.11 Study Visit, delayed start group only: Day 112/week 16

HCV VL and PBMC, plasma, serum, and Paxgene RNA for storage will be obtained. Safety assessment. **End of study participation.** Visit can be completed up to 2 days later.

6 Study Procedures/Evaluations

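### Section 4.2 lets a past positive HCV antibody qualify on its own, and no criterion requires the screening HCV RNA to be positive, so the active infection intended in Section 3.2 is not enforced by the eligibility list.

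*Combined protocol and SAP*

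**What the plan says.** Section 3.2 states the intended population: "Patients with HIV/HCV coinfection with HIV viral suppression and active HCV infection will be included".

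Section 4.2 puts the HCV part into a numbered criterion that asks only that the person be HCV-infected with no plan for HCV treatment during the study. It then defines HCV-infected by documentation at some point in the past of "Positive HCV antibody and/or positive HCV RNA test (HCV RNA of 2,000 IU/mL or greater"). On previous treatment, within its definition of DAA-naive, it adds: "Previous exposure to interferon and ribavirin are allowed".

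Section 5.1 says: "Outside labs performed within the last six months may be used to determine eligibility". Section 5.1.1 includes "Hepatitis C Quantitative RNA" among the screening labs, to be obtained within 6 months of study entry. Section 6.2, describing screening, makes hepatitis serologies and viral loads conditional on medical indication.

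The primary endpoint in the Protocol Summary is the change in HCV viral load from baseline to day 7. Section 11.2 analyses everyone who was enrolled and took at least one dose.

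**The concern.** The endpoint is a change in HCV viral load, so every analysed patient needs measurable HCV RNA at baseline. HCV antibody shows past exposure, not current viraemia. As written, a person with a positive antibody test years ago and no virus now meets the HCV definition. Such a person also readily meets the condition of having no plan for HCV treatment.

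Section 3.2 pairs HIV suppression with active HCV infection. The HIV half became a measurable criterion in Section 4.2: a viral load limit, a 12-month duration and a rule for a single blip. The HCV half has no counterpart. At stake is the primary estimate in a trial of 10 patients, where one patient is a tenth of the data.

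**Working it through.** **Step 1. Can a patient without HCV RNA meet every listed criterion?**

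- The Section 4.2 definition joins antibody and RNA with an and/or, so antibody suffices. The 2,000 IU/mL figure belongs to the RNA branch only.
- The documentation may be from any time in the past. Section 4.2 sets time limits for tests that show absence of cirrhosis, but none for HCV status.
- Previous interferon and ribavirin are permitted, and nothing in Section 4.2 or 4.3 excludes a person whose infection was cured or cleared.
- No numbered criterion in either section refers to the screening HCV RNA result.

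So the answer is yes, on the listed criteria.

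**Step 2. Does a later step close the gap by rule?**

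- *Randomization (Section 5.2).* "Enrolled participants will be randomized to the immediate start or delayed start group in a 1:1 fashion at time of enrollment". No viral load condition is attached.
- *Immediate start (Section 5.3.1).* The day 0 viral load is collected after eligibility is settled, at the same visit where dosing begins: "Maraviroc will be initiated for participants randomized to the immediate start group". It cannot act as a check before the first dose.
- *Delayed start (Sections 5.3.1, 5.6 and 5.8).* Viral loads are drawn at day 0 and week 4, before dosing at week 8. The week 8 step is: "A review of medical history and medication history will be performed to evaluate for any interim changes from screening visit". A physical examination is added, but nothing requires the earlier viral loads to be acted on.
- *Exclusion 3 (Section 4.3).* This covers a condition that the investigator regards as a contraindication. It is discretionary, and absent viraemia is not plainly a contraindication.
- *Section 9.4.* The investigator may request withdrawal at any time, but absent HCV RNA is not among the named reasons.
- *Appendix B.* Hepatitis C VL carries the same symbol in the screening column as CBC, creatinine and the hepatic panel. The key to that symbol is not in the text available, so nothing here rests on it.

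Discretion could catch such a patient. No rule does.

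**Step 3. Illustration of the effect on the estimate.**

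Inputs from the documents: N = 10 (Protocol Summary) and an expected drop of 1 log in seven days (Section 11.2). Assumptions: one of the 10 analysed patients has no HCV RNA, that patient's change is counted as 0, and the other nine each have the 1 log drop.

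Mean drop = (9 × 1 + 1 × 0) / 10 = 0.9 log.

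At the accrual ceiling of 15, with the same assumptions, it is (14 × 1 + 1 × 0) / 15 = 0.93 log.

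The plan has no stated figure to reproduce on this point. Section 11.1 gives no power, standard deviation or null proportion.

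**The case against.** The protocol, read as a whole, contains both the intent and the test. Section 3.2 states who will be included, Section 5.1.1 lists quantitative HCV RNA at screening, and Section 5.1 says recent outside labs may be used to decide eligibility. The numbered items about planned or imminent HCV treatment presuppose an infection to treat. An investigator who enrolled an RNA-negative patient would contradict Section 3.2, and exclusion 3 allows refusal before enrolment in both arms.

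Most of this stands as a reason to think the error unlikely in practice. It does not remove the gap: the listed criteria are what a screener applies, and they never say what the RNA result must be. The missing piece is a sentence linking the listed test to eligibility.

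Three stronger readings are tempting and are not supported.

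- A reader might infer that patients without viraemia will be enrolled in some number. The documents give no basis for a frequency.
- A reader might infer from Section 6.2 that the screening RNA is optional. It may instead govern only on-site testing when outside records are used. The text does not settle this, so the two sections need alignment and no more is claimed.
- A reader might infer a stated loss of power. The only test named in Section 11.2 is an exact one-sample binomial test, with no responder definition and no null proportion. A mean drop does not describe that test, and any power figure would rest on invented inputs.

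**Conclusion.** The point holds as a mismatch between Section 3.2 and the eligibility list, and it should be fixed. A person without current HCV RNA can satisfy every listed criterion, be dosed, and be counted in the primary analysis without being able to show a fall. The direction of the effect is toward zero.

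Confidence is high for the textual gap. The practical size is unknown. The 0.9 log figure is an illustration that depends on one such patient among 10 analysed, a zero change for that patient (the plan has no rule for an undetectable baseline) and a uniform 1 log drop in the rest. It is not a forecast.

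**What to change.** - In Section 4.2, remove the antibody-only route. Require quantifiable HCV RNA on the screening sample, or on an outside result within the existing 6-month window, taken after any previous HCV treatment.
- State whether the 2,000 IU/mL figure is kept as a floor. This point needs only a quantifiable result.
- Align the screening paragraph of Section 6.2 with Section 5.1.1, so that an HCV RNA result is always available before randomization.

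The cost is eligibility wording, because HCV RNA is already a listed screening test. Somewhat fewer patients will qualify; the documents do not say how many. Those lost for having no HCV RNA could not have informed the primary endpoint.
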